#### **9.1. Sample Size Determination**

A sample size estimate of 17,000 randomized subjects (8,500 on bococizumab and 8,500 on placebo) has approximately 90% power to detect a 20% reduction in the risk of experiencing the primary endpoint, by means of a two-sided  $\alpha = 0.05$  log rank test. The required number of subjects with an adjudicated and confirmed event is 844. The sample size calculation is based on an annual event rate of 2.3% and a premature study discontinuation rate of 1% per year. The trial is intended to complete after approximately 844 subjects have accrued an adjudicated and confirmed primary endpoint event (as defined in [Section 2.2.1](#)) or 12 months following the date that the last subject is randomized, whichever occurs later. Assuming that the trial will recruit in 3.1 years, with approximately 50% of the subjects in the last ten months, the study will finish in another approximately 1.7 years, for trial duration of approximately 4.8 years.

The sample size may be modified to shorten the expected duration of the trial or to improve the likelihood of attaining 70% power for the key secondary composite endpoint of CV death, non-fatal MI and non-fatal stroke. Prior to the end of enrollment, blinded assessments will be made of the expected duration of the trial and the power for this endpoint, assuming a hazard ratio of 0.8 and a two sided-alpha of 0.05. Under these assumptions, 496 confirmed and adjudicated events will provide approximately 70% power.

In addition, the sample size in certain subgroups, including diabetic subjects with no prior CVD event, may be modified or the trial duration may be extended to improve the likelihood that the estimated hazard ratios in the subgroups are less than one. Prior to the end of enrollment, the sponsor will perform a blinded assessment of the probabilities, assuming a hazard ratio of 0.8. Under this assumption, 58 events will provide approximately 80% probability that a point estimate is less than one.

As any adjustment to the sample size or duration of follow-up will be based on blinded data, the distribution of the test statistic for the primary analysis under the null hypothesis will not be affected and no alpha adjustment will be made.

These power and trial duration calculations were done with the software package EaST® (version 6.3.1).

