5.4.2.5. Subgroups for Anti-drug Antibody Titers and Neutralizing Antibody Titers

Time to first positive ADA result will be summarized in Treated Bococizumab Subjects With Positive ADA Status, which is defined in [Section 5.4.2.4](#) above. Time to first positive nAb result will be summarized in Treated Bococizumab Subjects with Positive nAb Status.

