8.2.4.1.1. Definitions

ADA and nAb titers are provided to Pfizer in log₂ format and will be reported in the same manner. All titles and labels used in tables and figures should clearly indicate titer (log₂).

ADA Measurement Level Status:

An ADA measurement is considered as ADA positive if the ADA titer ≥ 6.23 ; otherwise if non-missing, the measurement is considered as ADA negative.

nAb Measurement Level Status:

An nAb measurement is considered as nAb positive if the nAb titer ≥ 1.58 (Assay #2). An nAb measurement is considered as nAb negative if the ADA measurement from that sample is negative or if the nAb titer < 1.58 .

ADA Subject Level Status – For subject level classification of ADA (positive, negative):

A subject will be considered ADA positive if:

- The subject is ADA negative at baseline and has at least 1 ADA positive post-dose measurement, or
- The subject is missing the baseline ADA measurement and has at least 1 ADA positive post-dose measurement, or
- The subject is ADA positive at baseline and has a >1.58 unit increase in ADA titer from a positive baseline titer in at least 1 post-dose measurement.

A subject will be considered ADA negative if:

- The subject is ADA negative at baseline and all post-dose measurements are negative, or
- The subject is missing the baseline ADA measurement and all post-dose measurements are negative, or
- The subject is ADA positive at baseline but does not experience >1.58 unit increase in titer from a positive baseline titer in any post-dose measurement.

nAb Subject Level Status – For subject level classification for nAb (positive or negative):

A subject will be considered nAb positive if:

- The subject is nAb negative at baseline and has at least 1 nAb positive post-dose measurement, or
- The subject is missing the baseline nAb measurement and has at least 1 nAb positive post-dose measurement, or

- The subject is nAb positive at baseline and has a >1.58 unit increase in nAb titer from a positive baseline titer in at least 1 post-dose measurement.

A subject will be considered nAb negative if:

- The subject is ADA negative, or
- The subject is nAb negative at baseline and all post-dose measurements are nAb negative, or
- The subject is nAb positive at baseline but does not experience a >1.58 unit increase in titer from a positive baseline titer in any post-dose measurement.

ADA (nAb) Response Type:

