8.2.4.2. Summarization of ADA and nAb Results

1. The number of samples analyzed for ADA and nAb will be summarized.
2. ADA and nAb results will be summarized as categorical endpoints by visit and overall incidence at the subject level. The numbers and percentages of ADA positive and nAb positive subjects will be classified according to (1) timing of result with respect to bococizumab dosing (on treatment/off treatment), (2) characterization of ADA and nAb response (treatment induced/treatment boosted/indeterminate), and (3) duration of ADA and nAb response (indeterminate/persistent/transient) using the definitions in [Section 8.2.4.1.1](#) will be presented. The summary of nAb status will be performed with two different denominators: number of subjects with non-missing ADA samples and number of ADA positive subjects.

3. ADA titers for ADA positive subjects and nAb titers for nAb positive subjects will be summarized by visit as continuous endpoints. Boxplots of ADA titer and nAb titer over time will be presented for ADA positive subjects and nAb positive subjects, respectively.
4. Time to first positive ADA result and time to first positive nAb result will be summarized as continuous endpoints in subjects who are ADA positive or nAb positive, respectively.

A listing will also be provided that details subject identifier, treatment group, ADA titer, ADA status, nAb titer, nAb status, ADA induction type, nAb induction type, duration of ADA response, duration of nAb response, relative days to first positive ADA detection, relative days to first positive nAb detection, and day on study.

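### Overall ADA/nAb incidence and time to first positive are summarised without allowing for unequal follow-up, so both depend on when the program stopped; add a cumulative-incidence estimate

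*SAP*

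**What the plan says.** For incidence, SAP 8.2.4.2 states that "ADA and nAb results will be summarized as categorical endpoints by visit and overall incidence at the subject level". Under SAP 8.2.4.1.1 one positive post-dose sample is enough to classify a subject ("The subject is ADA negative at baseline and has at least 1 ADA positive post-dose measurement"), and no time horizon is set. The nAb percentages use subject counts as denominators ("number of subjects with non-missing ADA samples and number of ADA positive subjects"), not person-time.

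For timing, SAP 5.4.2.5 says "Time to first positive ADA result will be summarized in Treated Bococizumab Subjects With Positive ADA Status", with the same for nAb. SAP 8.2.3 repeats it, and under SAP 8.2.4.2 the two times "will be summarized as continuous endpoints in subjects who are ADA positive or nAb positive, respectively". SAP 8.1.1.2 makes a continuous summary a mean, standard deviation, median, quartiles and range, so no censoring is involved. Kaplan-Meier plots are planned for three clinical endpoints only (SAP 8.1.1.1).

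For follow-up, Protocol 9.1 assumes recruitment over 3.1 years, "with approximately 50% of the subjects in the last ten months", then about 1.7 further years. SAP 1.1 records that the development program was discontinued on 01 November 2016. SAP 8.2.2 notes that enrolment began slowly and that the latest visits will have few observations.

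A subject already positive at baseline also counts as ADA positive if "The subject is ADA positive at baseline and has a >1.58 unit increase in ADA titer from a positive baseline titer" in at least one post-dose sample. The SAP does not say which date is then the first positive result.

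**The concern.** Seroconversion is a time-to-event outcome. A subject followed for ten weeks can contribute only an early onset or a negative, whereas one followed for two years can contribute either an early or a late onset. A crude ever-positive share mixes the two, and an average taken only over those already positive leaves out every onset still to come. Both figures then move with the stop date even if the biology does not.

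The SAP was revised because of the stop, and it rewrote censoring for the clinical endpoints (SAP 7), but these two summaries were left without any such allowance. It gives clinical events rates per subject-year, and it gives discontinuation of study medication a log rank test and a Cox model (SAP 8.1.1.1, 8.2.4). Describing immunogenicity is a safety objective (Protocol 2.1.2.4; SAP 2.2), and a headline percentage without a time reference describes it poorly.

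**Working it through.** **The plan's own figure.** No ADA incidence or onset is stated for this trial. The only ADA figure is from three earlier studies (Protocol 1.2.3): 201/473 = 42.5%, which reproduces and is itself a crude percentage.

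**Inputs from the documents**
- Accrual: 3.1 years, half in the last ten months (Protocol 9.1).
- ADA samples: Weeks 4, 14, 40, 70, 104, 156 and 208, plus EDC/EOS (Protocol 6.4.2 to 6.4.4). The gaps are 10, 26, 30, 34, 52 and 52 weeks.
- Stop: 01 November 2016. The original protocol is dated 26 August 2013, 1,163 days earlier (1,163/365.25 = 3.18 years). Nobody could have been followed longer than that at the stop, against a planned trial duration of 4.8 years.

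**Assumptions**
- Entry as planned and a cut at 3.1 years, with a sample at the cut.
- Exponential onset among eventual responders, with median m of 6, 12, 26 or 52 weeks.

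**Follow-up.** A simulation of 400,000 subjects, with the first half entering over 2.27 years (flat or ramped), gives median follow-up of about 43 weeks. About 16% have under 14 weeks, 46% under 40 weeks and 54-57% under 52 weeks. At 4.8 years the median is about 132 weeks and nobody has under 52.

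**Crude incidence.** For flat accrual there is a closed form. Follow-up is uniform on 0 to a for half the subjects and on a to b for the other half, with a = 10/12 year = 43.5 weeks and b = 3.1 years = 161.8 weeks. With λ = ln 2/m, the share of eventual responders not yet positive is

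S = ½(1 − e^(−λa))/(λa) + ½(e^(−λa) − e^(−λb))/(λ(b − a)).

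For m = 6: λ = 0.1155, S = ½(0.1978) + ½(0.0005) = 0.099, so the crude share is 0.90. Cumulative incidence by Week 52 is 1 − 2^(−52/m) of eventual responders. The table adds the simulated ramped accrual where it differs.

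| Median onset (weeks) | S (flat) | Crude share / eventual responders | Crude share / Week 52 incidence |
|---|---|---|---|
| 6 | 0.099 | 0.90 | 0.90 |
| 12 | 0.189 | 0.81 | 0.85 |
| 26 | 0.344 | 0.64-0.66 | 0.85-0.87 |
| 52 | 0.520 | 0.45-0.48 | 0.89-0.96 |

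Moving the cut to three months after enrolment closes multiplies S by e^(−13λ). The flat-accrual shares become 0.98, 0.91, 0.76 and 0.56.

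The dependence on the stop date is plain at m = 26. The same biology gives a crude share 0.85-0.87 of Week 52 incidence at a 3.1-year cut and 1.29 of it at 4.8 years.

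**Time to first positive (simulated means, weeks)**

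| Median onset | Observed positives, 3.1-year cut | Complete follow-up, same visits | True mean onset |
|---|---|---|---|
| 6 | 13.7 | 15.8 | 8.7 |
| 12 | 21.5-21.9 | 27.2 | 17.3 |
| 26 | 31.3-33.9 | 49.9 | 37.5 |
| 52 | 39.0-44.7 | 77.5 | 75 |

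The reported mean is below complete follow-up in every row. Against true onset it is too late in the first two rows and too early in the last two.

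**The case against.** **This is a descriptive summary with other outputs beside it.** SAP 8.2.4.2 also gives by-visit results, a split by response type and duration, and a listing with "relative days to first positive ADA detection, relative days to first positive nAb detection, and day on study". An EDC/EOS sample is taken. Protocol 9.4 promised only the number and percentage positive, and the SAP delivers that. All of this stands and limits the importance. Even so, by-visit percentages are not cumulative incidence, and a listing is not an estimate.

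**Early onset may be likelier, and then the loss is small.** One of the three earlier studies treated for 24 weeks (Protocol 1.2.5). If all 473 subjects had been observed for 24 weeks, 42.5% positive would need an eventual share of 0.425/(1 − 2^(−24/m)). That is 0.45, 0.57 and 0.90 for medians of 6, 12 and 26 weeks, and an impossible 1.55 for 52. The durations of the other two studies are not given, so this leans towards earlier onset without settling it.

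Four stronger readings are tempting, and the documents do not support them:
- A reader might infer that about half the subjects were newly enrolled at the stop. The 50% is a planning assumption; the SAP's remark on slow early enrolment supports late weighting but not that share.
- A reader might infer that onset will look too early. That is certain only relative to complete follow-up on the same visits, as the second table shows.
- A reader might infer that the LDL-C analyses are compromised. SAP 8.2.4.3 uses antibody status, duration, pre-existing status and titer tertile, but neither the overall incidence nor the time to first positive.
- A reader might infer that boosted subjects are dated from their baseline sample. The SAP never says so; the date rule is simply undefined.

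**Conclusion.** The point holds as a modest improvement to a one-arm descriptive safety summary. As written, overall incidence and time to first positive depend on length of follow-up. Relative to complete follow-up on the same visits, the first is understated and the second shortened.

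Under the stated assumptions the incidence shortfall runs from about 10% of eventual responders (median onset 6 weeks) to 52-55% (52 weeks). Against Week 52 incidence it is 4-15%. Which end applies cannot be told from the documents: they give neither realised enrolment nor an onset distribution, and a later cut reduces the shortfall. The crude figure also cannot be set fairly beside the earlier 42.5% without knowing the follow-up behind each. No hypothesis test, alpha allocation or power figure is affected.

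**What to change.** Keep the planned crude, by-visit and listing outputs, labelled descriptive. In SAP 8.2.4.2, with matching wording in 5.4.2.5 and 8.2.3, add:
- Cumulative incidence of ADA, and separately of nAb, from first dose in all treated bococizumab subjects with a post-dose ADA sample. Use an interval-censored (Turnbull) estimate between last negative and first positive sample, or Kaplan-Meier by sample date. Censor negatives at their last ADA sample. The interval-censored version deals with visit spacing as well as truncation.
- Estimates with 95% confidence intervals at scheduled ADA visits such as Weeks 14, 40, 70 and 104, and the distribution of follow-up to last ADA sample.
- An onset rule for baseline-positive subjects: the first post-dose sample more than 1.58 units above baseline, matching the positivity rule in 8.2.4.1.1.
- A statement of whether positives first detected off treatment count, since 8.2.4.1.1 classifies them separately.

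The cost is a few lines of SAP text, one table and one plot. Days to first positive are already derived for the listing; the dates of the last negative and last ADA sample come from the same assay data.

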8.2.4.3. Summarization of Pharmacokinetics/Pharmacodynamics Results

The following analyses will be performed for LDL-C response. The windows from [Table 3](#) in [Appendix 1.1](#) will be used.

The following summaries will be provided using only observations meeting the following conditions (without missed doses and prior to dose adjustment):

- Sample collection date minus the previous injection date is between 1 and 21 days.
 - No dose adjustments have occurred prior to sample collection.
1. For LDL-C, the descriptive summaries will be repeated by ADA status and by nAb status. Box plots of percent change from baseline will be repeated by ADA status and by nAb status.
 2. For LDL-C, the descriptive summaries will be repeated by duration of ADA response (indeterminate/persistent/transient) and by duration of nAb response (indeterminate/persistent/transient). Box plots of percent change from baseline will be repeated by duration of ADA response (indeterminate/persistent/transient) and by duration of nAb response (indeterminate/persistent/transient).
 3. For LDL-C, the descriptive summaries will be repeated by pre-existing ADA status (with pre-existing ADAs, without pre-existing ADAs).
 4. For LDL-C, the descriptive summaries will be repeated by ADA (nAb) titer response (ADA (nAb) negative, ADA (nAb) 1st tertile, ADA (nAb) 2nd tertile, ADA (nAb) 3rd tertile).

A comprehensive listing of LDL-C, ADA status, ADA titer, nAb status, and nAb titer will be provided by subject and visit for ADA positive subjects.

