**Dosing windows:**

After randomization, investigational product dosing windows are 1 day before or up to 4 days after the scheduled dosing date. If more than 4 days after the scheduled day have passed, the subject should skip the dose and resume dosing following the dosing schedule provided by site personnel for the next injection.

**Visit 2, start of run-in:** Run-in Visit 2 can occur up to 14 days after Visit 1, depending upon the availability of Visit 1 lab results, additional medical records, if they are needed, and the schedule of the subject and clinical site. At Run-in Visit 2, the initiation of the run-in period, the subject will be shown how to self-inject investigational product (placebo). Only during the run-in period (Visits 2, 3, and 4), subjects will be seen up to two weeks apart, to ascertain the subjects' ability to self-inject investigational product. The other run-in procedures specified in this [Schedule of Activities](#) will be adhered to.

**Visit sequences:** After Visit 5 (Week 0) subjects will be seen at Visit 6 (Week 4), Visit 7 (Week 8), Visit 8 (Week 14), Visit 9 (week 26), Visit 10 (week 40), and Visit 11 (week 52). After Visit 11, subjects will be seen, as indicated in the [Schedule of Activities](#), until study completion (EOS). Subjects who discontinue investigational product early (EDC), will be encouraged to be followed, according to the visit schedule and activities, until study completion (EOS). If the study is not completed by Visit 20, visits will continue in accordance with the [Schedule of Activities](#) for annual (Visits 11, 14, 17, 20) and interim visits (eg, Visits 12, 13, 15, 16, 18, and 19), until study completion (EOS). The study may end sooner than Visit 20, if the primary endpoint event accrual rate is faster than anticipated or the trial is terminated for other reasons. Subjects who have had an investigational product (IP) dose frequency modification to dosing every 4 weeks, will need to have their visit frequency increased to every 8 weeks, approximately, for the purposes of direct LDL-C measurement and an assessment for adverse events, both serious and non-serious ([Section 6.4.5](#)). If the per-protocol scheduled visit falls within the 8 week window, the scheduled visit will reset the scheduling of the next 8 week direct LDL-C measurement visits.

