**Table 1. Treatments**

Group	
I	bococizumab, 150 mg SC, Q2wks
II	Placebo injection, SC, Q2wks

The IRT system will be used for each study visit during the active treatment period, to assign investigational product for each subject. For subjects who are randomized to the active treatment arm, blinded bococizumab will initially be administered at a dose of 150 mg SC Q2wks. For subjects who are randomized to placebo, blinded placebo will initially be administered SC Q2wks. Blinded dose modifications may take place, through the IRT system, based on trigger measurements of LDL-C (5.4.1.1).

At Visit 5, after the subject has been randomized, and all other procedures and assessments completed, the first active treatment period dose will be self-injected or injected by a care-giver at the clinic. The subject will be observed, at the study site, by the study site personnel, for 30 minutes after the injection. Subjects will be provided with a dosing schedule by site personnel based on the date of randomization. Subjects will receive sufficient pre-filled syringes (PFSs) to self-inject between clinic visits. As noted in the [Schedule of Activities](#), many of the scheduled doses will also coincide with scheduled visits. When a scheduled dose occurs on the same day as a scheduled visit, subjects should hold their self-injected dose until they are at the clinic and self-inject or be administered an injection by a care provider only after all other study procedures for that visit have been completed.

Injections 1 day before or up to 4 days past the scheduled day of administration are allowed. If more than 4 days after the scheduled day have passed, the subject should skip the dose and resume dosing following the dosing schedule provided by site personnel for the next injection.

Subjects should adhere to their treatment schedule even if their scheduled clinic visit is rescheduled or missed due to unforeseen circumstances.

Subjects will continue to receive their prescribed, background lipid lowering therapy, at the dose that they had taken at the last visit of the run-in period prior to the randomization visit.

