### **Scheduling:**

The visit window for all post randomization visits will be  $\pm 14$  days, except for visits 8, 11, for which the visits windows are  $\pm 3$  days, and EDC/EOS visits, which will not have visit windows. Study sites should attempt to schedule each subject's visits at the same time of day for that subject. Visits should be scheduled based on the week in the [Schedule of Activity](#) Table and coordinated with the subject's dosing schedule, so that the visit day is coordinated with a subject's relevant dose day, if possible. Starting at Visit 5, and all subsequent visits, if a visit coincides with a scheduled injection of investigational product, the injection should be performed after all other study procedures have been completed.

Ideally, after randomization, visits should be scheduled to take place on a dosing day, so that dosing can take place at the end of the study visit. Lipid level tests (direct LDL-C and lipid panel) should be scheduled no sooner than 10 days after the subject's prior dose, even if this requires an unscheduled visit. If a subject has a visit that is scheduled less than 10 days after the last dose, the visit procedures may take place, but lipid labs should be postponed and drawn at the earliest possible time, at an unscheduled visit, no sooner than 10 days after the last dose.

Subjects will be required to fast (water only) for at least 10 hours prior to all study visits during which blood samples will be collected, with the following exceptions. Unscheduled assessments limited to measures of CK, liver function tests (including ALT, AST, alkaline phosphatase, and total and direct bilirubin), hepatitis C PCR testing, or pregnancy testing, do not require fasting. Subjects should take prescribed permitted concomitant medication, as needed, prior to each study visit if it can be administered with water only; prescribed permitted concomitant medications that must be taken with food or after meals should NOT be taken until after the visit procedures have been completed. Subjects who do not fast will be required to return for fasting laboratory tests, at the earliest possible time, before the next scheduled study visit.

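### The SAP's LDL-C summaries by antibody status are labelled as free of missed doses, but the filter checks only the last injection and admits samples drawn before the 10-day minimum

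*SAP*

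**What the plan says.** SAP 8.2.4.3 restricts the LDL-C summaries and box plots by ADA/nAb status and response duration, and the summaries by pre-existing ADA and titer tertile, to observations described as "without missed doses and prior to dose adjustment". Two conditions implement that description: "Sample collection date minus the previous injection date is between 1 and 21 days" and "No dose adjustments have occurred prior to sample collection".

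The regimen before any adjustment is "bococizumab, 150 mg SC, Q2wks" (Protocol Table 1). Under Dosing windows in the Schedule of Activities footnotes, "investigational product dosing windows are 1 day before or up to 4 days after the scheduled dosing date"; a dose later than that is to be skipped. Protocol Section 8.4 separately says that a single out-of-window dose is not a medication error if at least 7 days separate it from the nearest dose.

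On sampling, Protocol Section 6 (Scheduling) says that post-randomization lipid tests "should be scheduled no sooner than 10 days after the subject's prior dose". SAP Appendix 2 repeats this rule and applies it to ADA samples as well.

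**The concern.** The label makes an adherence claim that the rule does not deliver. The interval to the last injection says nothing about the injections before it, so a subject who has just restarted counts as fully dosed. At the lower end, the filter accepts samples from a part of the dosing interval in which sites are told not to draw.

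These displays describe whether antibodies weaken the LDL-C response. Subjects with recent gaps in dosing may show smaller reductions for reasons unrelated to antibodies, and LDL-C depends on the time since injection. If either differs between antibody groups, the tables could show an apparent antibody effect or hide a real one. If neither differs, the result is dilution and noise.

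Nothing else in the SAP closes the gap:
- The analysis windows in SAP Table 3 count from randomization, not from a dose.
- Protocol deviations do not affect inclusion (SAP 5.6).
- The treatment-adherent analyses were removed (SAP 1.1).
- Bococizumab and PCSK9 samples will not be assayed (SAP 6.3.1), so no drug level can show who was under-exposed.
- The compliance percentage in SAP 6.3 is not used here. It also leaves out doses withheld because of adverse events.

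**Working it through.** The plan gives no figure to reproduce. The check compares the filter with the dosing and sampling rules.

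**Inputs.** Filter: 1 to 21 days (SAP 8.2.4.3). Interval: 14 days (Protocol Table 1). Dosing window: -1 to +4 days (Dosing windows). Sampling minimum: 10 days (Protocol Section 6; SAP Appendix 2). Week 14 visit window: ±3 days (Protocol Section 6).

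**1. Earlier doses.** Take the day-0 dose as given, six doses due on days 14, 28, 42, 56, 70 and 84, and a Week 14 sample on day 95, 98 or 101.
- Patterns with at least one miss: 2^6 - 1 = 63.
- If the day-84 dose was taken, the gap is 11, 14 or 17 days and the observation passes whatever happened before. Such patterns with at least one earlier miss: 2^5 - 1 = 31.
- If the day-84 dose was missed, the gap is at least 95 - 70 = 25 days and the observation fails.

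So 31 of 63 patterns pass, the extreme being five of six doses missed. This counts patterns; it is not a frequency. The documents give no miss rate. If each dose is missed independently with probability q, the share of Week 14 observations with the last dose taken but at least one of the five earlier doses missed is 1 - (1 - q)^5:

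| q (assumed) | share |
|---|---|
| 2% | 10% |
| 5% | 23% |
| 10% | 41% |
| 20% | 67% |

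**2. Lower bound.** Days 1 to 9 fall below the 10-day minimum: 9 of the 21 admitted days. This too counts days, not observations.

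**3. Upper bound.** The longest gap with both doses inside the window is (14 + 4) - (-1) = 19 days, so days 20 and 21 lie outside the dosing window. Under Protocol Section 8.4, however, a late dose that still leaves 7 days before the next scheduled one can fall at 28 - 7 = 21 days after an on-time dose. A sample at day 20 or 21 may therefore precede a late dose rather than follow a missed one.

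**4. Whether timing matters.** In the Phase 2b study (Protocol 1.2.5), the Q4wks differences in LDL-C ranged from -27.8 to -45.2 mg/dL at the end of the interval and from -46.8 to -55.5 mg/dL when nadir and trough were averaged. Assume that the range ends pair by dose. The implied nadir is then 2 × (-46.8) + 27.8 = -65.8 and 2 × (-55.5) + 45.2 = -65.8 mg/dL. The effect lost between weeks 10 and 12 is 65.8 - 27.8 = 38.0 or 65.8 - 45.2 = 20.6 mg/dL. These are other doses at a longer interval, so they show only that time since injection matters. They do not size an effect here, and they say nothing about days 1 to 9.

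**The case against.** The strongest reply is that these are descriptive summaries of post-randomization subgroups, with no test, alpha or decision rule, and that the SAP already urges caution for ADA/nAb subgroups (5.4.2.2, 5.4.2.3). Further immunogenicity analyses are placed in a separate SAP (Section 3). The filter removes the most obvious case, a missed latest dose with the visit on a dosing day. Early draws should be uncommon, because visits are coordinated with dosing and sites are told to postpone them. All of this stands and limits the importance of the point. It does not make the label true. The planned by-visit listing does not help either: it covers only ADA-positive subjects, and injection dates are not among its stated contents.

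A reader might go further in three ways that the documents do not support.
- **That days 20 and 21 prove a missed dose.** They are outside the dosing window, but Section 8.4 tolerates a single late dose at that distance.
- **That the antibody comparison is biased.** Bias needs adherence or draw timing to differ by antibody status, and no document reports either. A link is conceivable, since injections may be stopped after hypersensitivity reactions (Protocol 7.2.7.2), but it is not shown.
- **That the count of out-of-rule days measures the affected data.** Draws probably cluster near day 14, and their distribution is not given.

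**Conclusion.** The concern holds in a limited form. The filter in SAP 8.2.4.3 does not deliver the absence of missed doses that its label states, because no dose before the last injection is checked. It also admits days 1 to 9, against a sampling minimum that the SAP itself repeats. Both follow from the text without assumptions. LDL-C differences by antibody status can therefore be mixed with recent non-adherence and draw timing.

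How much mixing occurs, and in which direction, cannot be determined from the documents. The shares of 10% to 67% rest on assumed, independent miss rates of 2% to 20% per dose, and they describe mislabelled observations, not LDL-C bias. The primary analysis, the key secondary tests and the error rate are unaffected.

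**What to change.** In SAP 8.2.4.3:
- Set the lower bound at 10 days since the previous injection.
- Add a short look-back using actual injection dates from the dosing CRF, for example that the previous three scheduled doses were all taken. In the Week 14 enumeration this requires the doses on days 56, 70 and 84, which leaves 2^3 - 1 = 7 of the 63 patterns passing, all with misses at least 98 - 42 = 56 days before a day-98 sample.
- State the reason for the upper bound. Dosing windows gives a maximum in-window gap of 19 days, while Section 8.4 allows for a later single dose. The two passages need to be reconciled for the purpose of defining a missed dose in this analysis.
- If the 1-to-21-day version is wanted, keep it as a second display without the missed-dose label.

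Do not require that no dose was missed since randomization. With independent misses of 2% or 5% per dose, 0.98^25 = 60% or 0.95^25 = 28% of subjects would remain at Week 52 (25 doses after the first), and 0.98^51 = 36% or 0.95^51 = 7% at Week 104 (51 doses). It could also remove antibody-positive subjects preferentially if their interruptions relate to antibodies. A short look-back carries a milder form of the same risk.

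The cost is one sentence and a programming filter, because the date of each dose is already collected (SAP 6.3). Among observations with the latest dose taken, the three-dose look-back keeps (1 - q)^2 = 96%, 90%, 81% or 64% for assumed miss rates of 2%, 5%, 10% or 20%. The 10-day bound removes a further number that the documents do not allow to be estimated.
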